## 10. SAFETY ANALYSES

Safety analyses will be conducted using the Safety Population including by treatment groups and total OCA (both OCA 25 mg and OCA 10 mg combined). If a subject is randomized to placebo and subsequently receives OCA, each TEAE (Section 10.3) will be attributed to the administered OCA dose.

No inferential comparison of safety endpoints will be performed, unless otherwise specified.

There will be 2 sets of safety summaries presenting the safety profile of the following populations:

1. The Safety Population as defined in Section 3.4
2. The ITT population as defined in Section 3.4

Frequencies of adverse events will be split into 2 periods: pre-Covid 19 (occurring on or before 30 Jan 2020) and post-Covid 19 (occurring after 30 Jan 2020). The data for both periods will be presented side-by-side by treatment group for the safety population.

Selected safety summaries will be prepared including all subjects in the mITT Efficacy Population. Summaries and listings will be presented by actual treatment received.

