### **3.4.2. End of Study Analysis Populations**

- The Safety Population will include all randomized subjects who received at least 1 dose of investigational product (OCA or placebo). Treatment assignment will be based on the treatment actually received.
- The Full Efficacy Analysis Population will include all randomized subjects, all fibrosis stages (stages 1, 2 and 3), who received at least 1 dose of investigational product. Treatment assignment will be based on the randomized treatment.
- The Intent-to-Treat (ITT) Population will be a subset of the Full Efficacy Analysis Population, limited to those subjects with fibrosis stage 2 or stage 3. Treatment assignment will be based on the randomized treatment. The ITT Population will be the primary efficacy analysis population. The Per Protocol (PP) Population will include all subjects from the ITT Population who did not have any major protocol deviation ([Section 5.5](#)) that could potentially affect the efficacy conclusions and at least 80% compliance with investigational product ([Section 10.1](#)). Treatment assignment will be based on the randomized treatment.
- The PK Population will include all subjects who received OCA and have at least one confirmed fasted analyzable sample. Subjects must have been fasting for approximately 8 hours before the visit and must not have any major protocol deviations that potentially affect exposure levels. The PK Population will be used for OCA PK.

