### 10.3. Adverse Events

AE data will be collected from the time that signed informed consent is obtained until the subject fully completes her/his study participation of the study. AEs will be reported and categorized using the Common Terminology Criteria for Adverse Events (CTCAE, Version 4.03).

All AE summaries will be restricted to TEAEs, which are defined as any AEs that newly appear, increase in frequency, or worsen in severity following randomization up to 30 days from the last dose date of permanent investigational product discontinuation up to new data cut-off date. If it cannot be determined whether the AE is treatment emergent due to a partial onset date, then it will be counted as such. Verbatim terms on eCRFs will be mapped to preferred terms (PT) and system organ classes (SOC) using MedDRA version 18.1 or later version.

Each AE summary will be displayed by treatment group. Summaries that are displayed by SOC and PT will be ordered by descending order of incidence (OCA 25 mg, followed by OCA 10 mg, followed by placebo) of system organ class and preferred term within each system organ class. Summaries of the following types will be presented:

- Overall summary of TEAEs
- Subject incidence of TEAEs and the total number of entries by MedDRA SOC and PT.
- Subject incidence of TEAEs and the total number of entries by PT in descending order.
- Subject incidence of serious TEAEs and the total number of entries by MedDRA SOC and PT.
- Subject incidence of TEAEs leading to investigational product withdrawal by MedDRA SOC and PT.
- Subject incidence of TEAEs leading to study discontinuation by MedDRA SOC and PT.
- Subject incidence of TEAEs by MedDRA SOC, PT, and highest severity (CTCAE grade). At each level of subject summarization, a subject is classified according to the highest severity if the subject reported 1 or more events. AEs with missing severity (CTCAE grade) will be considered grade 3 (severe) for this summary.
- Subject incidence and total number of entries of CTCAE grade 3 or higher TEAEs by MedDRA SOC and PT. At each level of subject summarization, a subject is

classified according to the highest severity if the subject reported 1 or more events. AEs with missing severity (CTCAE grade) will be considered grade 3 (severe) for this summary.

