**Exposure-adjusted incidence rate (EAIR)** difference (with corresponding 95% Cis) will be calculated for the number of subjects with any event by subcategory of interest as well as for each PT. EAIR will be calculated to correct for differences in investigational product exposure by using person-time in the denominator. Adjusted incidence per 100 SEY is defined as the number of subjects with an event for whom person-time is available divided by the total SEY for each treatment group and multiplied by 100. If a subject experiences the event of interest, the subject's SEY will be calculated as (first event onset date, minus the first dose date plus 1) divided by 365.25 days/year. If a subject does not experience the event of interest, the subject's SEY will be calculated as (earliest date of the last dose date plus 30 days or study discontinuation date or death date or date cut-off date minus the first dose date plus 1) divided by 365.25 days/year. One SEY is the equivalent of one subject exposed to investigational product for one year. Two subjects who are exposed to investigational product for half a year together contribute one SEY. The total SEY of a treatment group is the sum of the SEY for each subject in that treatment group. Exposure-adjusted incidence rates will be calculated for each treatment group. Exposure-adjusted incidence rate difference and the corresponding 95% CI will be derived from Poisson regression model with treatment as explanatory variables.

The time to onset of first treatment-emergent AESI, including onset of first treatment-emergent AESI with different categories, will be estimated using the KM method by calculating the time from the first dose date to the first occurrence of a specific category of treatment-emergent AESI. Subjects who do not experience an event will be censored as described in General Statistical Methods ([Section 4](#)).

The duration of first treatment-emergent AESI and most severe treatment-emergent AESI will be estimated using the KM method by calculating the time from the start date of first occurrence of a given treatment-emergent AESI or most severe AESI to its resolution (AE outcome being "recovered/resolved" in the eCRF). If the AESI remains ongoing, subjects will be censored as described in General Statistical Methods ([Section 4](#)). Only subjects with the events will be included in the analysis.

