Added Analysis of Covid-19 impact on the study	Following FDA guidance: Conduct of Clinical Trials of Medical Products During the COVID-19 Public Health Emergency	Impact of Covid-19 on protocol deviations under section 5.6  Incidence of Covid-19 infection under section 10.3  Incidences of AEs before and after Covid-19 under section 10.
Updated lab analysis	Per FDA feedbacks, additional lab data analyses related to cardiovascular, renal and hepatic injuries from both local and central laboratories have been produced in Month 18 IA resubmission and will be also done at the end of study	Updated Serum Chemistry Lipids analysis under section 10.4.9.4  Updated Liver Injury related lab data analyses under section 10.5.4.  Updated Renal injury related lab data analyses under section 10.5.6

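### The before/after-COVID adverse-event table has no per-period exposure adjustment, so it can mislead between arms if discontinuation differs and between periods in any case

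*SAP*

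**What the plan says.** SAP Section 10 (Safety Analyses) sets up the table: "Frequencies of adverse events will be split into 2 periods: pre-Covid 19 (occurring on or before 30 Jan 2020) and post-Covid 19", the latter meaning events after that date. It then adds: "The data for both periods will be presented side-by-side by treatment group for the safety population". Section 3.4.2 defines the end-of-study Safety Population as everyone randomized and dosed at least once; being treated or followed after the cut is not required.

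Section 10.3 adds two rules. "All AE summaries will be restricted to TEAEs", and the treatment-emergent window runs "up to 30 days from the last dose date of permanent investigational product discontinuation".

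Exposure adjustment appears in Section 10.4, for adverse events of special interest: "EAIR will be calculated to correct for differences in investigational product exposure by using person-time in the denominator". There a subject's time stops at the first event or, without an event, at last dose plus 30 days (or earlier study discontinuation, death or data cut-off). EAIRs are also planned for adjudicated events and liver laboratory criteria. None of these is split at 30 Jan 2020.

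Section 11 describes the output as "Incidences of AEs before and after Covid-19 under section 10", so it is meant to be read as incidence.

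**The concern.** Together these rules leave the post-period table with subjects who cannot contribute to it. Anyone permanently off drug more than 30 days before the cut is in the named population but outside the event window. Subjects who stop during the post period contribute only part of it. Nothing in the table corrects for either.

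Two comparisons are affected, in different ways.

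- **Between arms.** If one arm loses more subjects from treatment, its post-period frequency falls for that reason, and a real excess can look like parity.
- **Between periods.** The two periods need not be equally long, and staggered entry gives subjects different amounts of pre-period time. A before/after difference then mixes exposure with any change in risk, even if discontinuation is identical across arms.

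This is the only planned before/after comparison of adverse events overall, so a reader asking whether the pandemic changed the safety picture would turn to it.

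**Working it through.** The plan gives no figure for this table, so there is none to reproduce. The check below is an illustration.

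**Inputs, all assumed.** First-event rate λ = 0.30 per year, equal in both arms and constant. Permanent discontinuation d = 0.08 per year (arm A) and 0.15 (arm B). First dose uniform between 0.3 and 4.3 years before the cut. Post period T = 3 years. The 30-day tail is left out; including it moves the full-population percentages by about 0.4 points (to 45.3% and 35.9%).

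**Step 1. Share still on drug at the cut.** f = [exp(−0.3d) − exp(−4.3d)] / (4d).
- A: (0.9763 − 0.7089)/0.32 = 0.835
- B: (0.9560 − 0.5247)/0.60 = 0.719

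**Step 2. Probability of an on-treatment post-period event, given on drug at the cut.** I = λ/(λ+d) × [1 − exp(−(λ+d)T)].
- A: 0.30/0.38 × (1 − 0.3198) = 53.7%
- B: 0.30/0.45 × (1 − 0.2592) = 49.4%

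**Step 3. Percentage of the full Safety Population.** f × I.
- A: 0.835 × 0.537 = 44.9%
- B: 0.719 × 0.494 = 35.5%

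The gap is 9.4 points and the ratio 0.79, with no true difference. The ratio factors as 0.719/0.835 = 0.86 (losses before the cut) times 0.494/0.537 = 0.92 (losses after it). An at-risk denominator removes only the first factor and leaves 53.7% versus 49.4%.

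**Step 4. EAIR by the Section 10.4 rule, restricted to the post period.** Subject-years to first event or stopping, per subject at risk: [1 − exp(−(λ+d)T)]/(λ+d).
- A: 0.6802/0.38 = 1.790, so 0.537/1.790 = 0.30
- B: 0.7408/0.45 = 1.646, so 0.494/1.646 = 0.30

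Both arms show 30 per 100 subject-years.

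**Step 5. Masking.** Give arm B a true rate 40% higher (0.42 per year): I = 0.42/0.57 × (1 − 0.1809) = 60.4%, and f × I = 43.4%. Arm B still looks slightly better than arm A's 44.9%.

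**Step 6. Range for the arm comparison**, same formulas.

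| Discontinuation per year, A vs B | λ per year | Full-population %, A vs B |
|---|---|---|
| 8% vs 8% | 0.30 | 44.9 vs 44.9 |
| 8% vs 10% | 0.30 | 44.9 vs 41.9 |
| 8% vs 12% | 0.30 | 44.9 vs 39.2 |
| 8% vs 15% | 0.05 | 10.4 vs 8.1 |
| 8% vs 15% | 0.30 | 44.9 vs 35.5 |
| 8% vs 15% | 1.00 | 74.3 vs 60.5 |

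The false gap shrinks to zero as the discontinuation rates equalise.

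**Step 7. Before versus after, within one arm.** With d = 0.08 and λ = 0.30 throughout, the pre-period percentage, averaged over entry, is 0.30/0.38 × {1 − [exp(−0.114) − exp(−1.634)]/(0.38 × 4)} = 42.7%. The post-period percentage is 20.9%, 35.1% or 44.9% for a post period of 1, 2 or 3 years. The same constant risk can therefore look like a halving or a slight rise, depending only on period length.

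**The case against.** The strongest reply has five parts.

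1. **The denominator is not written out.** This is true: Section 10 names a population, not a divisor, and table shells are not in the documents. But the Safety Population is the only population offered, and the general percentage rule in Section 4 (non-missing data) would not remove subjects who are off drug. Raw counts would be distorted in the same direction.

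2. **Discontinuation by arm is unknown.** This stands. A reader might infer that the obeticholic acid arms will look falsely safe. The documents make unequal discontinuation plausible: Protocol Section 5.3 reports pruritus in 23% versus 6% in the earlier Phase 2 study, Protocol Table 4 ties Grade 3 or worse pruritus to stopping product, and SAP Section 3.4.1 records a rise in discontinuations in late 2017. They give no rates by arm, so neither direction nor size can be asserted.

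3. **Other COVID analyses exist.** This stands. A reader might take the table for the plan's only check on the pandemic. It is not: SAP Section 5.6 separately summarises COVID-related treatment-emergent events and protocol deviations.

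4. **Late entry and period length cannot bias the arms.** Correct under concurrent 1:1:1 randomization. They affect only the before/after comparison.

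5. **The plan has safeguards.** Section 10 plans no inferential safety comparison unless specified. Events of special interest get EAIRs with confidence intervals and time-to-onset curves over all exposure, and exposure and withdrawals are reported by arm. These lower the stakes, but none is split by period and the EAIRs do not cover all adverse events.

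**Conclusion.** The concern holds in a conditional form. As written, the table has no per-period exposure adjustment, and the treatment-emergent window guarantees that subjects already off drug cannot have post-period events. If discontinuation differs by arm, the arm with more of it shows a post-period frequency that understates its on-treatment rate. In the assumed scenario this is about 45% versus 36% with equal true rates, and a 40% excess is hidden. With equal discontinuation the arm comparison is undistorted, but the before/after comparison remains uninterpretable.

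The size rests entirely on assumed discontinuation, event rate, entry pattern and period length. It also rests on reading the named population as the denominator. Because the table is descriptive, the consequence is a misleading impression, not a wrong test. The change is worth making but does not threaten the trial's conclusions.

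**What to change.** In SAP Section 10, make the main measure of this table the per-period EAIR per 100 subject-years, by arm. Use the Section 10.4 rule restricted to each period: count subjects with a first event in the period; start time at the later of first dose and period start; stop it at that event, at last dose plus 30 days or the other Section 10.4 censoring dates, or at period end. Show at-risk N and subject-years for each arm and period in the column headers.

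If percentages are kept, base them on subjects in the treatment-emergent window during that period and label them as not exposure-adjusted. In the scenario above, the at-risk denominator alone still leaves about 54% versus 49%.

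One limit should be noted with the table: a per-period EAIR assumes a roughly constant rate within the period and does not remove selection of subjects who tolerate treatment.

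The cost is SAP wording and a small amount of programming, since the EAIR is already defined. No endpoint, alpha allocation or trial procedure changes.

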### 10.1. Extent of Exposure

The extent of exposure will be summarized both continuously using descriptive statistics and categorically (n and % for  $\leq 4$  weeks,  $>4$  and  $\leq 12$  weeks,  $>12$  and  $\leq 24$  weeks,  $>24$  and  $\leq 36$  weeks,  $>36$  and  $\leq 48$  weeks,  $>48$  and  $\leq 72$  weeks,  $>72$  and  $\leq 96$  weeks,  $>96$  weeks  $\leq 120$  weeks;  $>120$  weeks  $\leq 144$  weeks,  $>144$  weeks  $\leq 168$  weeks,  $>168$  weeks  $\leq 192$  weeks). After Month 48 (Week 192) until the end of the study, exposure will be presented by 48 weeks periods.

Extent of exposure (days) to investigational product will be calculated as follows:

- Exposure to investigational product =  $\{[(\text{Date of last investigational product dose} - \text{Date of 1}^{\text{st}} \text{ investigational product dose}) + 1] - \text{Total duration of temporary investigational product discontinuation, interruption, drug holidays and/or missed doses}\}$

The duration of each incidence of temporary investigational product discontinuation will be calculated as follows:

- Duration of temporary discontinuation, interruption, and/or missed doses of investigational product =  $(\text{Date of restart of investigational product} - \text{Date of temporary discontinuation, interruption, drug holidays and/or missed doses of investigational product}) + 1$ .

The total duration of temporary investigational product discontinuation is the sum duration of temporary discontinuation, interruption, and/or missed doses of investigational product over each incidence of discontinuation / interruption.

Total investigational product (mg) exposed to subject will be calculated by adding the doses taken by a subject during the study and will be summarized using descriptive statistics.

A summary of subjects who had an at least one temporary investigational product interruption, discontinuation, and/or missed doses (including drug holiday) during the study will be provided in terms of frequency count (n) and percentages (%) and mean duration of the interruptions/missed doses. This summary will be presented by reason of interruption as specified in the eCRF.

Subject's overall compliance (%) with investigational product will be calculated as follows:

- $(\# \text{ of tablets consumed during study} / \# \text{ of tablets expected to be consumed during study}) * 100$

where # of tablets consumed during study = # of tablets dispensed- # of tablets returned or

- $\text{total investigational product (mg) exposed to subject} / \text{total investigational product (mg) planned}$

where total investigational product planned = (End date of IP exposure – Start date of IP exposure + 1)

Subject compliance with investigational product will be summarized by treatment group using descriptive statistics. For discontinued subjects, the expected tablets to be consumed will be calculated based on the time of discontinuation.

All exposure data will be presented in a by-subject data listing.

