Figure 3: Algorithm for Determining Progression to Cirrhosis

CP = Child-Pugh; INR = international normalized ratio; IP = investigational product; NFS = nonalcoholic fatty liver disease fibrosis score; TE = transient elastography; ULN = upper limit of normal.

Note: To maintain blinding, dose adjustments will be handled by the investigational product supplier such that:

- Subjects on OCA 25 mg have the dose reduced to OCA 10 mg
- Subjects on OCA 10 mg and placebo remain on OCA 10 mg and placebo, respectively

^a It is not necessary to rule out the occurrence of varices, ascites, or hepatic encephalopathy at each visit; however, if at any time during the clinical management of the subject there are signs and symptoms that are suggestive of any of these events (eg, ascites noted on ultrasound or presence of varices noted on clinically indicated EGD), then the subject is considered to have met the criteria for progression to cirrhosis and a Child-Pugh screen must be assessed for that subject.

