Investigational product should **not** be interrupted in the following instances: 1) in subjects who previously experienced an event of symptomatic cholelithiasis and/or cholecystitis, and in whom symptoms have fully resolved at the present time while on investigational product; 2) in subjects who experience an event that is not symptomatic (such as an incidental finding of gallstones during an ultrasound exam); 3) in subjects who have already undergone a cholecystectomy following a prior event of cholelithiasis or cholecystitis (and who have no symptoms suggestive

of retained or recurrent bile duct stones); or 4) in subjects who have a medical history of pancreatitis and have not experienced a recurrence of pancreatitis since enrollment into the study.

Table 4: Criteria for Dose Adjustment, Interruption, Discontinuation and Rechallenge

DOSE ADJUSTMENT		
Criteria	Action Taken with IP	Rechallenge
Progress to cirrhosis and have Child Pugh A cirrhosis (CP score <7)	Adjust to a maximum daily dose of 10 mg (or equivalent placebo) in a blinded fashion	Not applicable. Remain at maximum daily dose of 10 mg (or equivalent placebo) for remainder of study.
≤Grade 2 Pruritus (refer to Section 15.1.5.1)	Drug holiday or less frequent dosing, as needed	Return to original daily dose if tolerated
DOSE INTERRUPTION		
Criteria	Action Taken with IP^a	Rechallenge^b
Liver laboratory values ^c are above the upper threshold criteria and signs and symptoms of hepatic injury are present ^d	Interrupt immediately upon initial observation	Subject may be rechallenged after a minimum of 30 days if abnormal liver enzymes return to below threshold values, there are no symptoms, laboratory abnormalities are determined not to be due to DILI and approved by the Medical Monitor and Investigator. If the liver enzymes do not return to below threshold values after 30 days and the Investigator considers that the event has not resolved, the Investigator should consult with the Medical Monitor to determine a treatment plan. This may include continuing close monitoring with interruption or discontinuing investigational product.
Liver laboratory values ^c are above the upper threshold criteria and there are no signs and symptoms of hepatic injury ^d	According to threshold limits (Table 2), either interrupt or interrupt after confirmation by repeat testing	

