15.1.5.1. Severity of Pruritus (as an AE)

To ensure consistency in reporting, pruritus AEs must be graded for severity (ie, intensity) using the current version of the CTCAE ([Appendix D](#)) the category definitions are included in [Table 11](#) for reference. As pruritus is a subjective symptom, clinical judgment should be used to determine its management.

Table 11: Severity of Pruritus

Pruritus Grade	Clinical Description of Severity for Pruritus
1 = Mild	Mild or localized; topical intervention indicated.
2 = Moderate	Intense or widespread; intermittent; skin changes from scratching (eg, edema, papulation, excoriations, lichenification, oozing/crusts); oral intervention indicated; limiting instrumental activities of daily living.
3 = Severe	Intense or widespread; constant; limiting self-care activities of daily living or sleep; oral corticosteroid or immunosuppressive therapy indicated.

Since pruritus is a subjective symptom, the occurrence and magnitude of which are not readily measured objectively, clinical judgment needs to be applied in the management of each subject. Managing OCA-related pruritus may help improve tolerance in those subjects who experience problematic pruritus and may otherwise discontinue from the study prematurely. Guidance for the management of subjects experiencing significant pruritus are provided in [Table 4](#) ([Section 7.7](#)) and includes:

- Pruritus \geq Grade 3 in severity: Discontinue investigational product
- Pruritus \leq Grade 2 in severity: One or more of the following may be considered:
 - Drug holiday or less frequent dosing at the discretion of the Investigator.
 - Short-term use of BAS

- Use of BAS may be considered in conjunction with a change in investigational product dosing frequency (ie, every other day dosing) for approximately 2 weeks. The subject should be evaluated after the 2-week intervention to assess the status of pruritus and stop the use of BAS as deemed appropriate by the Investigator. If the Investigator considers that the subject can tolerate investigational product, daily dosing may be reinitiated.
 - If the subject cannot tolerate investigational product after stopping BAS due to ongoing pruritus, the Investigator should consult with the Medical Monitor to determine a treatment plan. This may include continuing every other day dosing, interrupting, or discontinuing investigational product.

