**Table 3: Analysis Populations for the Month 18 Interim Analysis and End of Study Analysis**

Population	Fibrosis Stage	Description	
		Month 18 Interim Analysis	End of Study
Safety	1,2 and 3	Randomized subjects who received at least one dose of investigational product by the DCO (IA Cohort)	Randomized subjects who received at least one dose of investigational product.
Full Efficacy Analysis	1,2 and 3	All subjects, randomized by 15 July 2017, all fibrosis stages (stages 1, 2 and 3), who received at least 1 dose of investigational product.	Randomized subjects who received at least one dose of investigational product.
ITT	2 and 3	Subset of Full Efficacy Analysis Population	Subset of Full Efficacy Analysis Population
mITT	2 and 3	Subset of ITT Population which excludes treatment discontinuation (before the Month 18 Visit and without an end of treatment biopsy) between 13 Sep 2017 to 19 Dec 2017 due to withdrawal of consent, lost to follow up and other reasons	Not applicable
Per Protocol	2 and 3	Subset of ITT Population who completed at least 15 months of treatment, had a Month 18/end of treatment biopsy, were on investigational product for at least 30 days just preceding the biopsy, and did not have any major protocol deviation	Subset of ITT Population with no major protocol deviation and at least 80% compliance with investigational product ( Section 10.1 )

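### SAP 10.1's milligram compliance formula divides by days and cannot support the 80% End-of-Study Per-Protocol rule; interruption length and the non-diabetic group carry smaller derivation errors

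*SAP*

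**What the plan says.** **Compliance.** SAP 10.1 gives overall compliance as a percentage in two ways joined by *or*. The first is tablets consumed (dispensed minus returned) over tablets expected, times 100. The second is total milligrams exposed over total milligrams planned. The numerator is in milligrams: "Total investigational product (mg) exposed to subject will be calculated by adding the doses taken by a subject during the study". The denominator is spelled out as "where total investigational product planned = (End date of IP exposure – Start date of IP exposure + 1", after which the bracket closes. The only further rule is in tablets: "For discontinued subjects, the expected tablets to be consumed will be calculated based on the time of discontinuation".

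**Where compliance is used.** SAP 3.4.2 admits a subject to the End-of-Study Per-Protocol Population on condition of "at least 80% compliance with investigational product" and points to 10.1. SAP Table 3 repeats it: "Subset of ITT Population with no major protocol deviation and at least 80% compliance with investigational product". Neither names a formula.

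**Permitted departures from daily dosing.** For lower-grade pruritus, Protocol 7.7 Table 4 allows "Drug holiday or less frequent dosing, as needed", and Protocol 15.1.5.1 adds "This may include continuing every other day dosing, interrupting, or discontinuing investigational product". For progression to cirrhosis, the Figure 3 notes in Protocol 7.4.2 state "Subjects on OCA 25 mg have the dose reduced to OCA 10 mg".

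**Interruptions.** SAP 10.1 sets the length of each interruption as restart date minus interruption date, plus 1, and subtracts the total from exposure days.

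**Diabetes.** SAP 10.4.8 counts a subject as diabetic at baseline if any one of three things holds: history, antidiabetic medication for diabetes, or HbA1c of at least 6.5%. Its bullet on starting antidiabetic medication describes the non-diabetic group by the three negatives, also joined by *or*.

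**The concern.** A population rule needs one derivation that gives the same answer whoever programs it. Here the rule leads to two formulas, and the second is not a percentage: its units are milligrams per day, so its value depends on the assigned dose as well as on adherence. Placebo subjects score zero however many tablets they take. Anyone repairing it must make a choice that the plan did not make, and a choice that decides membership of an analysis population should be made before unblinding.

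The other two items are of the same kind but smaller: a day count that is one too long under the SAP's own record convention, and a definition that is not the complement of the one it is meant to negate.

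**Working it through.** The documents contain no worked compliance, interruption or diabetes-group figure, so there is nothing to reproduce. The check applies each rule as written.

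**1. Compliance**

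Inputs: one tablet daily of placebo, 10 mg or 25 mg (Protocol 9.1); the 80% threshold (SAP 3.4.2, Table 3); the formulas in SAP 10.1. Let D be days from first to last exposure and a the fraction of daily tablets taken.

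- Tablet version: a·D / D × 100 = 100a in every arm. Full adherence gives 100%.
- Milligram version as written: (dose × a·D) / D = dose × a. At a = 1:

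| Arm | Tablet version | Milligram version as written |
|---|---|---|
| OCA 25 mg | 100% | 25 |
| OCA 10 mg | 100% | 10 |
| Placebo | 100% | 0 |

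- Against 80, no arm can pass, since the maximum is 25. Against 0.80, OCA 25 mg passes from 0.80/25 = 3.2% adherence, OCA 10 mg from 0.80/10 = 8%, and placebo never.
- With planned milligrams corrected to dose × D and the ratio multiplied by 100, the OCA arms on a constant dose agree with the tablet version. With D = 336 taken as an example, 269 tablets give 269/336 = 80.1% both ways. Placebo becomes 0/(0 × D) = 0/0, so the milligram version still cannot serve that arm.

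The tablet version works in all arms but leaves one detail open: whether days of a permitted hold or of reduced-frequency dosing count as expected. If one tablet is expected on every day, a subject dosed every other day for a share x of treatment time scores 1 − 0.5x, which is below 80% once x exceeds 0.40. If the off days are not expected, the same subject scores 100%. This is missing detail, not an error.

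**2. Interruption length**

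Input for the date convention: SAP Appendix A imputes a missing exposure start as the preceding record's stop plus one day, and a missing stop as the following record's start minus one day, with interruptions and drug holidays included among the records. Records therefore abut: a hold starts on the first missed day, and the next dosing record starts on the first day back.

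Take a hold on days 5 to 9, true length 5, with dosing resumed on day 10.

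- First missed day to first day back, SAP formula: 10 − 5 + 1 = 6, one too many.
- First missed day to last day off: 9 − 5 + 1 = 5, correct.

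With 28-day months (Protocol 9.9.1), one excess day per gap understates exposure by 1/504 = 0.20% at Month 18 (18 × 28 = 504) and 1/1344 = 0.07% at Month 48 (48 × 28 = 1344). If the pruritus bins of SAP 10.4.1 (1–5, 6–10, over 10 days) use this formula, true 5-day and 10-day gaps move up one bin. That section does not say which formula the bins use.

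**3. Non-diabetic group**

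Three yes/no criteria (history, medication, HbA1c at or above 6.5%) give 2 × 2 × 2 = 8 combinations.

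- Diabetic (any criterion met): 7 of 8.
- Non-diabetic as written (any criterion not met): 7 of 8. Only the combination with all three criteria met is excluded.
- Overlap: 6 of 8 are both diabetic and non-diabetic, for example a subject with a history, on medication, and HbA1c below 6.5%.
- Negatives joined by *and*: 1 of 8, no overlap.

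These are logical cells; they say nothing about how many subjects fall in each.

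**The case against.** The strongest reply is that the text already leans towards tablets. Only the tablet version is multiplied by 100, the one rule that follows both formulas speaks of expected tablets, and Protocol 9.4 bases accountability on counting returned tablets. A programmer would probably notice scores of 25, 10 and 0. A dose factor may also have been lost when the PDF was read. All of this lowers the practical risk and supports a minor rating. It does not remove the point: the *or* is unresolved, the population rule names no formula, and a restored dose factor would still leave placebo at 0/0.

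Three stronger readings are tempting and are not supported.

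- A reader might infer that 25 mg subjects who progress to cirrhosis would fall out of Per-Protocol because their dose is reduced. That requires planned milligrams to stay at 25 mg per day after the reduction. No passage says so, and Protocol Table 4 caps the daily dose at 10 mg for the remainder of the study, so planned milligrams would naturally follow it.
- A reader might infer a two-day over-count per interruption. That requires the interruption date to be the last dosing day, which conflicts with the abutting records in Appendix A. Because Appendix A is an imputation rule and not a definition, even the one-day figure is conditional on it.
- A reader might take SAP 4.4 as showing that End-of-Study Per-Protocol feeds subgroup analyses of the primary endpoint. That list reads as Month 18 text: it includes the mITT Population, which Table 3 marks as not applicable at End of Study, and a key secondary endpoint that the SAP labels only for Month 18. Protocol 16.8 specifies ITT for subgroups at both the interim and the final analyses.

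**Conclusion.** The point holds as a minor one: three rules are wrong as written. The milligram compliance formula cannot support the 80% rule in any arm as printed, nor in the placebo arm after the obvious repair. The interruption formula is one day too long per gap if restart is the first day back and the hold starts on the first missed day. The non-diabetic bullet overlaps the SAP's own diabetes definition in 6 of 8 combinations.

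The reach is limited to membership of the End-of-Study Per-Protocol Population, which the protocol synopsis uses only for supportive analyses; to descriptive exposure and interruption tables; and to one descriptive incidence of starting antidiabetic medication. Any further use of that population in SAP 6.2.3 (Sensitivity Analyses) cannot be judged, because that section's text is not in the available copy.

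Nothing here touches the End-of-Study primary analysis, which SAP 6.4.4.2 runs on ITT. Month 18 Per-Protocol has its own criteria without the 80% rule. The exposure-adjusted rates in SAP 10.4 take person-time from dates without subtracting interruptions.

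**What to change.** 1. State in SAP 3.4.2, Table 3 and 10.1 that the tablet formula governs the 80% rule in all arms. Delete the milligram version, or keep it as a descriptive summary for the OCA arms only, with the denominator equal to the planned daily dose in force on each day summed over planned days, and the ratio multiplied by 100. In the same edit, state whether days of protocol-permitted holds and reduced-frequency dosing count as expected tablets.
2. In SAP 10.1, define the interruption date as the first missed day and restart as the first dosing day, and drop the added 1. Alternatively, use the last day off in place of the restart date and keep it.
3. In the antidiabetic-initiation bullet of SAP 10.4.8, join the three negatives with *and*, so that the group is the complement of the SAP's diabetes definition.

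The cost is SAP wording and the matching programming specification. No new data are needed, and dosing and clinical management do not change. The edits should be made before the End of Study data are unblinded.
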